### **11.2 Follow-up Procedures After Withdrawal**

Participants who prematurely discontinue study medical device are not to be replaced.

All randomized participants must be followed up according to the study flowchart until study end date or death, regardless of whether they discontinued study medical device prematurely or not. Any event occurring after early study medical device discontinuation will be recorded up through the study end date.

In case of study medical device discontinuation (temporary or permanent) due to an adverse event, such participants will be closely monitored until the resolution or stabilization of this adverse event. This may mean that follow-up will continue after the participants have completed the study follow-up. Although data on that adverse event will continue to be captured, even beyond the last visit, for new efficacy or safety events, only those that occur up through the last visit should be recorded.

In case of written withdrawal of consent (WOC) for follow-up visits, and unless otherwise stated by the patient in the informed consent form, Investigators will be encouraged to get information from the general practitioner, any other physician, or other medical-care provider, in order to follow the medical status of the participants (especially when they withdraw their consent after having experienced an AE/SAE or an efficacy endpoint). Investigators will also be expected to try as much as possible to re-contact those participants at the end of the trial, in order to obtain at least their follow-up of the efficacy assessment.

For participants considered lost to follow-up, the CRF must be completed up to the last visit performed.

### **11.3 Consequence**

If the medical device is stopped prematurely, every attempt should be made to restart it if medically appropriate, whatever the duration of discontinuation.

If the patient withdraws his/her consent for study participation, although in such circumstances he/she may not be obliged to comply with all the protocol visits and phone calls, the Investigators, the study nurses and any other study coordinators are requested to try to obtain as much as possible, the vital status of the patient at study end date. This will be clearly stated in the informed consent form.

Any direct communication with the general practitioner, any other physician or other medical-care provider can be helpful for following the medical status of the patient. This is particularly important if the patient withdraws his consent after experiencing an AE/SAE or an efficacy endpoint since for safety and Regulatory purposes, it is necessary to obtain some information regarding worsening or resolution of the event (especially if this event is considered as to be related to the Investigational Product).

In addition to the need for safety assessment, it is also important to avoid any lost to follow-up participants for the efficacy assessment and meaningful analysis of the study.

## **12. STUDY PROCEDURES**

### **12.1 Visit Schedule**

After initial contact and pre-qualification through enrollment in person. The participant shall be provided with an appointment for enrollment. Patient shall provide full medical history with any known pulmonary, cardiovascular or neurological diagnosis. This decision shall be that of the PI and the clinical health care provider at the location of the trial.

#### **12.1.1 Pre-Screening Procedures**

Study participants will be recruited from email list recruitment, clinics, and diagnostic centers, under the responsibility of a participating Investigator. Prior to initiation of the recruitment phase, participating Investigators will identify a pool of potential study subjects. Each of these centers will identify potentially eligible participants in advance,

#### **12.1.2 Baseline Visit**

The patient will receive complete information about the study in writing and orally if they choose. Written informed consent must be obtained from the patient prior to any study-specific procedures and prior to randomization. Compliance with inclusion criteria (listed in Section 7.2) and exclusion criteria (listed in Section 7.3) will be checked on the basis of information collected, and recorded in the CRF.

Key baseline patient characteristics obtained at the randomization visit will be recorded in the CRF, including demographics, height, weight, relevant past medical and surgical history, including neurological and psychiatric history, and abnormalities noted on physical exam, including any past dermatology exams.

Medical history, physical examination, laboratory, or instrumental results confirming inclusion and absence of exclusion criteria will be maintained in the participant's file.

## **12.2 Inclusion Procedures**

Once all inclusion/exclusion criteria are fulfilled, the patient becomes eligible for randomization and inclusion into the treatment period. Treatment allocation will be performed as stated above (Section 8.3). Study kit will be delivered as stated in Section 8.4.

Participants will be counseled to follow a healthy diet, to increase their water consumption and to stop smoking, if they are smokers.

## **12.3 Description by Type of Visit**

- Baseline enrollment form completed and submitted online (secure site), informed consent signed and submitted.
- Follow up call, email and follow up summary completed by the Investigator at the end of the one month treatment period with written results.
- Three (3) month participant courtesy email to confirm safety and answer any questions.

**There is no strict timing for the phone calls. In any case, it is better to call the patient after a delay, than to not call them at all (even in this case, the phone call record page of the CRF should be completed).**

The patient visit schedules will be given by the Investigator as soon as the participant is randomized, so as the Investigator can plan in advance all the necessary appointments with the participant.

## **12.4 Definition of Source Data**

All the data collected in the CRF come from source documents that are part of the patient dossier. Copies of some of those source documents will be collected after anonymization, in order to support documentation of outcome events eligible for validation by the Clinical Events Committee, ie:

.

## **13. STATISTICAL CONSIDERATIONS**

### **13.1 Statistical and Analytical Plans**

The material of this section is the basis for the Statistical Analysis Plan of this study. This plan may be revised during the study to accommodate Clinical Trial Protocol Amendments and to make changes to adapt to unexpected issues in study execution and data that affect planned analyses. These revisions will be based on blinded review of the study and data, and a final plan will be issued prior to data lock.

### **13.2 Determination of Sample Size**

Based on the targeted population for the study of 30,000 patients, 70 participants is considered a reasonable assumption for the yearly representational event rate in the group. Assuming recruitment over a 16 month period, and a total study duration of 24 months, 70 participants per group has been historically significant for prior trials designed to illustrate clear efficacy of a device as it relates to the United States CMS for this category of device.

### **13.3 Study Patient Description**

No specifics other than the trial inclusion parameters.

#### **13.3.1 Disposition of Participants**

The number of randomized participants will be summarized by county and center using counts and percentages. The number of participants either completing or permanently discontinuing the study medical device period will be summarized using counts and percentages.

#### **13.3.2 Clinical Trial Protocol Deviations**

All the following deviations will be summarized on the all randomized patient population:

- Inclusion or exclusion criteria not satisfied.
- Deviations related to the study medical device administration
- Not permitted concomitant medications.

## **13.4 Data Analysis Considerations**

### **13.4.1 Dataset Analyzed**

#### **13.4.1.1 Treatment Group Considered for Statistical Analysis**

For all efficacy and safety analyses, participants will be included in the treatment group to which they were originally allocated by the PI.

#### **13.4.1.2 Populations to be Analyzed**

The intent-to-treat (ITT) population will be used for all efficacy and safety analyses. This will consist of all randomized participants irrespective of whether the patient actually received study medical device or the participant's compliance with the study protocol, in the treatment group assigned by the software system. A patient will be considered randomized as soon as they are assigned to the group, after proper consent.

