## **6.3 Interim Analysis**

Interim analysis during this study shall be conducted at Day 7, 14 and 21 for the 70 participants to ensure participant safety before the other participants enter into the trial.

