### **8.3 Method of Assigning Participants to Treatment Group**

N/A - All included shall be assigned to the single arm.

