## **Adverse Events**

All Adverse Events regardless of seriousness or relationship to Investigational Product, including those from the first visit planned in the Clinical Trial Protocol/signature of the informed consent form, are to be recorded on the corresponding page(s) included in the Case Report Form. Whenever possible, symptoms should be grouped as a single syndrome or diagnosis. The Investigator should specify the date of onset, intensity, action taken with respect to Investigational Product, corrective treatment/therapy given, outcome and his/her opinion as to whether there is a reasonable possibility that the Adverse Event was caused by the Investigational Product.

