#### **13.7.1.1 Description of the Primary Variable(s)**

The primary efficacy endpoint is the composite cluster of the first occurrence, over the duration of study (randomization to study end date inclusive), of the following adjudicated events:

- Any skin conditions caused by the device to include irritations,
- Any allergic reactions,
- Any new medical conditions during the study.

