#### **13.7.1.2.3 Main Statistical Model and Adjustment for Covariates**

For the primary analysis, all adjudicated events occurring from randomization to the study end date (inclusive) will be counted, including events occurring after early permanent discontinuation of study medical device. The proportion of participants remaining event-free over time will be displayed in the form of survival curves using the Kaplan-Meier method and analyzed (primary analysis) using a two-sided log-rank test. Statistical significance will be claimed if the computed p-value is equal to or less than 0.05.

The number and percentage (crude rate) of participants experiencing a primary endpoint will be summarized.

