### **13.8 Safety Analysis**

For this morbidity/mortality trial, a benefit risk assessment is important. For this purpose safety analyses will be conducted on the same population (ITT) and using the same evaluation period as for efficacy analyses. (ie, from randomization until study end date)

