Statistical and Analytical Plan:

All study practices and statistical methods are based on the International Conference on Harmonization (ICH) document "Statistical Principles for Clinical Trials."

Data will be summarized by treatment group. Baseline characteristics, and safety outputs total overall columns will be included to summarize all subjects.

For all baseline, demographic, safety and efficacy outputs data will be summarized by treatment group.

In summary tables of continuous variables, the minimum and maximum statistics, the arithmetic mean and median, the 95% confidence interval, standard deviation, and standard error will be presented will to the same number of decimal places as the original data.

In summary tables of categorical variables, counts and percentages will be used. The denominator for each percentage will be the number of subjects within the population treatment group unless otherwise specified.

All hypothesis testing will be carried out at the 5% (2-sided) significance level unless otherwise specified.

P-values will be rounded to three decimal places. P-values less than 0.001 will be reported as <0.001 in tables.

At the conclusion of the trial, the raw data shall be analyzed by a blinded statistician of Mack Biotech, Corp. and then create a report with the clinical trial outcome.

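### Safety is analysed only in all assigned participants from assignment to study end; a single-arm trial also needs a treated safety set and an on-device adverse-event table.

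*Protocol*

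**What the plan says.** Protocol section 13.4.1.2 names one analysis population for efficacy and safety alike. It consists of "all randomized participants irrespective of whether the patient actually received study medical device", and a participant enters it on assignment to the group, after consent. Section 13.4.1.1 likewise covers efficacy and safety together. Section 13.8 states that "safety analyses will be conducted on the same population (ITT) and using the same evaluation period as for efficacy analyses", that is, from randomization to the study end date. The adverse-event sections (13.8.1.1 to 13.8.1.4) define neither a treatment-emergent nor an on-device period.

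The SAP names no analysis set. It says only that "The denominator for each percentage will be the number of subjects within the population treatment group unless otherwise specified", so its default denominator follows the protocol's intention-to-treat set.

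There is one arm. Section 8.3 says "All included shall be assigned to the single arm".

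Recording of adverse events (section 10.1) starts earlier than the analysis window, "including those from the first visit planned in the Clinical Trial Protocol/signature of the informed consent form".

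**The concern.** Intention-to-treat analysis protects a randomized comparison. Here there is nothing to compare, so the adverse-event percentages can only serve to describe risk with the device. Two things blur that description.

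- **Population.** Anyone assigned who never uses the device adds to the denominator but cannot have a device-caused event.
- **Window.** Events between assignment and first use, and events after last use, are counted together with events during use. With no second arm, such background events do not cancel.

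The first effect lowers the percentage of device-caused events. The second raises the percentage with any event. The net direction is unknown, and a reader of the planned tables could not undo either effect.

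**Working it through.** **Nothing to reproduce.** The documents give no expected adverse-event rate, no never-user share and no date on which device use ends. The only figure taken from the plan here is 70 participants (sections 7.1 and 13.2). The remaining inputs are labelled assumptions.

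**1. Population effect.** Assume 10 participants with an event and none among never-users. The percentage is 10 / n.

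| Never used (assumed) | Denominator | Percentage |
|---|---|---|
| 0 of 70, or all assigned counted | 70 | 14.3% |
| 4 of 70 | 66 | 15.2% |
| 7 of 70 | 63 | 15.9% |

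The exact 95% interval for 10/70 is 7.1% to 24.7%, so the shift lies well inside sampling error. It is zero if everyone uses the device.

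**2. The window in the documents.** The relevant statements do not agree:

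- Section 6.2: 21 active days per participant, but follow-up to a common end date two months after the last entry, with recruitment written as both one and two weeks.
- Sections 8.10 and 13.8.3: a 21-day trial.
- Section 12.3: a one-month treatment period.
- Section 13.2: 16 months of recruitment within 24 months.
- Section 11.2: events after early device discontinuation recorded to the study end date, but, for participants followed beyond the study because of an adverse event, new events only up to the last visit.
- Section 13.6.1.2: compliance is days of use divided by days of follow-up, which may imply use throughout follow-up.

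None of these states when device use ends.

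**3. Window effect, illustration only.** Assume that use ends at day 21 and follow-up runs as in section 6.2. With a month of 30.44 days, uniform entry and two weeks of recruitment, follow-up runs from 2 × 30.44 = 60.9 days to 60.9 + 14 = 74.9 days, mean 67.9. The share on device is then 21 / 67.9 = 30.9%. With one week of recruitment the mean is 64.4 days and the share 32.6%.

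At an assumed background rate r per person-year, the chance of at least one background event by day t is 1 − exp(−r × t / 365.25). For the last column this is averaged over 60.9 to 74.9 days.

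| r (assumed) | By day 21 | By one month (30.4 days) | Section 6.2 follow-up |
|---|---|---|---|
| 0.5 | 2.8% | 4.1% | 8.9% |
| 1 | 5.6% | 8.0% | 17.0% |
| 2 | 10.9% | 15.4% | 31.0% |

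At r = 1 the ratio is 17.0 / 5.6, about threefold; in people, 70 × 0.056 = 3.9 against 70 × 0.170 = 11.9. If recording stops at a one-month last visit, the ratio is 8.0 / 5.6, about 1.4. If use continues through follow-up, most of the window is on-device and the gap is much smaller.

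**The case against.** The best defence has four parts.

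- **The choice is deliberate.** Section 13.8 wants benefit and risk on the same population and period, and full follow-up catches late harms. This stands as a reason to keep the full table, but not as a reason to have only that table.
- **Never-users may be few or absent.** Participants must already be prescribed a home airway clearance device (section 7.2), and the kit is delivered at inclusion (section 12.2). This stands, and it is why the population effect is called small.
- **Partial information exists.** Each adverse event carries a causality opinion and the action taken (section 10.1). Exposure and patient-years are summarized (13.6.1.1), as are device-related events (13.8.1.2) and events leading to discontinuation (13.8.1.4). Safety looks "shall be conducted at Day 7, 14 and 21 for the 70 participants to ensure participant safety". These help, but none sets a treated denominator or an on-device window for the final tables.
- **The size rests on assumed rates.** It does, and the table above is not a forecast.

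Three stronger readings are tempting, and the documents do not support them. A reader might infer that every event from consent onwards enters the safety tables. Section 10.1 governs recording, whereas the window in 13.8 begins at assignment, so events between consent and assignment are recorded but fall outside it. A reader might infer that about two thirds of follow-up is off-device. That needs use to stop at day 21, which no section states. A reader might also conclude that the primary analysis should move to treated participants, because its composite includes "Any new medical conditions during the study" and counts events to study end, "including events occurring after early permanent discontinuation of study medical device". Section 13.7.1.2.1 requires all randomized participants in that analysis, so the move would create a new contradiction.

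**Conclusion.** The point holds for the safety analyses of section 13.8. They use only the all-assigned set and the full window, in a design where that protects no comparison, and no treated set or on-device window is defined in either document. The population effect is small (14.3% against 15.9% with 7 assumed never-users of 70) and may be zero. The window effect is unknown. It ranges from little, if use continues through follow-up, to about threefold for background events if use ended at day 21 and section 6.2 follow-up applied. A reader might infer that the plan understates device risk. The documents do not support a direction, because dilution and background events pull opposite ways. Severity is minor to moderate; the case for acting is that the change is cheap and the resulting table answers a question that the planned tables cannot.

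**What to change.** 1. In section 13.4.1.2 define a Safety set of participants with at least one device use. Amend 13.4.1.1, 13.4.1.2 and 13.8 so that the safety analyses use it, and name the set in the SAP.
2. In section 13.8 add an adverse-event table running from first use to last use plus a pre-stated number of days. Keep the all-assigned, full-follow-up table beside it, so that early and late events stay visible.
3. Report how many assigned participants never used the device.
4. Record the dates of first and last use on the CRF. The returned-bottle count in section 8.10 cannot date device use.
5. Leave the primary Kaplan-Meier analysis (13.7.1.1 and 13.7.1.2.3) on the all-assigned set that 13.7.1.2.1 requires. A Safety-set version may be added as supportive only.
6. Reconcile sections 6.2, 8.10, 11.2, 12.3, 13.2, 13.6.1.2 and 13.8.3 so that one use period and one event window apply. This review does not say which is right.

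The cost is wording, one extra table and two dates per participant. Onset dates, treatment duration and days of use are already planned. Percentages of device-caused events may look slightly less favourable on the smaller denominator.

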#### **13.4.1.3 General Statistical Approach**

All statistical tests will be two-sided.

All summary tables for quantitative parameters will display mean, standard deviation, median, range (minimum and maximum), as well as number of missing data (if relevant). All summary tables for qualitative parameters will display counts, percentages and number of missing data if relevant.

Baseline data are defined as the last measurement performed before the first study medical device intake.

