#### **4.3 Rationale for this Trial Design**

Since this study is designed to illustrate the efficacy of the device for the current 510K indications in a single arm, large sample multisite study. A placebo control is not required since each subject will serve as a before and after treatment with measurable indicators.

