### **5. STUDY OBJECTIVES**

#### **5.1 Primary Objective**

To specifically illustrate and measure both clinical and empirical efficacy described by (AARC) in the Clinical Practices Guidelines for Postural Drainage Therapy (1991) for external manipulation of the thorax for postural drainage therapy and the secretion clearance, or presence of atelectasis caused by mucus plugging.

Outcome measured by:

Percentage change of oxygen levels in the blood (pulse oximetry). SpO2 will be monitored using the standard pulse oximeter system (K131111). Change from baseline before treatment and measure again up to 3.5 hours after treatment.

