### **8.11 Participant Reimbursement**

Participants shall be reimbursed at a rate of seven dollars (\$7.00) per day for each day that data for the two objectives is sent to the Principal Investigator. The reimbursement is provided for the participant's time for recording the data on a personal smart device, the cost of data transfer and overall phone costs for sending the information to the Principal Investigator. The total reimbursement amount that may be provided to the participant is no more than \$210.00. The reimbursement shall be provided to the participant, by the Sponsor, after the participant completes the trial period by company check paid to the participant.

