### **9.1.1 Efficacy Criteria**

Primary: Physical exam by medical practitioner for initial diagnosis and changes in spirometer reading from before treatment compared to reading three (3) hours after treatment. In addition, changes in iHealth Air pulse oximeter (FDA 510k K131111) reading from before treatment compared to reading three (3) hours after treatment.

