#### **9.1.1.2 Secondary Criterion**

Percent change of spirometer reading from before treatment compared to three (3) hours after treatment by the participant. Subjective participant opinion of the efficacy provided by semi-weekly surveys.

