#### **13.6.1.2 Measurement of Treatment Compliance**

Treatment compliance for each patient will be calculated as the number of days study medical device was actually used (ie, number of days on treatment minus days of temporary discontinuation) divided by the number of days of follow-up, allowing for early permanent discontinuation of study medical device when applicable. Study medical device discontinuation is defined as a minimum of 3 consecutive days without study medical device intake. The percentage of participants at least 80% compliant will also be reported.

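### Section 13.7 plans only first-event methods, which cannot analyse the SpO2 and spirometry changes that define efficacy; the reference reading and post-treatment time also need settling

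*Protocol*

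**What the plan says.** Protocol 4.3 justifies the single arm on the ground that "each subject will serve as a before and after treatment with measurable indicators". Section 5.1 takes percentage change in SpO2 as the primary outcome, and 5.2 takes percentage change in FVC and FEV1 as the secondary. Both specify "Change from baseline before treatment and measure again up to 3.5 hours after treatment". Section 9.1.1 lists spirometry and oximetry together as primary, each as the change in "reading from before treatment compared to reading three (3) hours after treatment". Section 9.1.1.2 has "Percent change of spirometer reading from before treatment compared to three (3) hours after treatment by the participant", plus participant surveys.

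Section 13.7 sets out something different. In 13.7.1.1, "The primary efficacy endpoint is the composite cluster of the first occurrence, over the duration of study", and the events are skin conditions, allergic reactions and new medical conditions. The methods are:

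- 13.7.1.2.3: Kaplan-Meier curves, a two-sided log-rank test and a crude rate.
- 13.7.1.2.5: Cox models with treatment and treatment-by-covariate terms.
- 13.7.1.2.1: censoring of participants without an event at their last assessment.
- 13.7.2.2: the same methodology for the secondary endpoints, except weight and waist circumference.

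Section 8.3 places everyone in one arm.

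On the reference reading, 13.4.1.3 states: "Baseline data are defined as the last measurement performed before the first study medical device intake". This is the only baseline definition in either document. Reimbursement in 8.11 is paid "for each day that data for the two objectives is sent to the Principal Investigator", and compliance in 13.6.1.2 counts "the number of days study medical device was actually used", so use on several of the 21 days is expected. The SAP adds generic summaries of continuous variables with a 95% confidence interval, and a two-sided 5% level. It names no test, reference reading, session or time point.

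**The concern.** The outcomes collected and the analysis prescribed do not meet. A change in SpO2 or FEV1 is a continuous quantity built from a pair of readings, whereas survival methods need an event and a time. An analyst who follows 13.7 would work on the event composite and leave the stated efficacy outcomes untested. Section 13.7.1.2.4 allows the secondary tests only after the primary reaches significance, so a primary test that cannot be computed blocks those as well.

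The test, the reference reading, the sessions and the measurement time would then be chosen late. Section 13.1 promises a final plan before data lock, revised on blinded review. In a single arm, however, every reading is known to be on the device, so blinding does not stop these choices being made after the changes have been seen.

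**Working it through.** **1. The plan's own figure.** Section 13.2 gives 70 participants. The documents state a two-sided 5% level but no effect size, SD, event rate, power or dropout figure, so 70 cannot be reproduced.

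**2. Log-rank test with one arm.** At an event time with d events among n at risk, n1 of them on the device, the expected number is d × n1/n and the variance is proportional to (n1/n)(1 − n1/n). With one arm n1 = n, so expected = d, observed − expected = 0, and the variance factor is 1 × 0 = 0. The statistic is 0/0 and there is no p-value. The usual event-count formula divides by p(1 − p), where p is the share allocated to the device; at p = 1 this is division by zero.

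**3. Cox models with one arm.** The treatment indicator equals 1 for everyone, so its multiplier cancels from every term of the partial likelihood and no hazard ratio can be estimated. The treatment-by-covariate product equals the covariate itself, so the interaction cannot be separated from it.

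**4. Method against outcome.**

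- Event composite (13.7.1.1): Kaplan-Meier and the crude rate work in one arm as description. The log-rank test and the Cox treatment terms do not.
- Change in SpO2, FVC and FEV1 (5.1, 5.2, 9.1.1, 9.1.1.2): no method in 13.7 applies, and censoring has no meaning for a missing before/after pair.

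**5. Reference reading.** Let pre_1 be the reading before first use, and pre_k and post_k the readings around session k. Let a be the same-session change and b the shift in the pre-treatment level since session 1.

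- Absolute: post_k − pre_1 = (post_k − pre_k) + (pre_k − pre_1) = a + b.
- Percent: post_k/pre_1 − 1 = (1 + a)(1 + b) − 1 = a + b + ab.
- Session 1: b = 0, so the two references agree.
- Later session with a = b = 2% (both assumed): 0.02 + 0.02 + 0.0004 = 4.04%, against 2% from the same-session reference.

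**6. Post-treatment time.** A reading at three hours satisfies all four sections. A reading at ten minutes satisfies 5.1 and 5.2, which give no lower limit, but not 9.1.1 or 9.1.1.2, which give no tolerance.

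**7. What a paired analysis would give.** With n = 70, the half-width of the 95% CI is t/√n = 1.995/8.367 = 0.238 SD of the change. At an assumed 80% power, a two-sided 5% paired test detects 0.34 SD. With 49 complete pairs (an assumed 30% missing) it detects 0.41 SD. These stay in SD units because the documents give no SD.

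**The case against.** The strongest reply concerns the two definitions. Section 13.4.1.3 is a general convention, placed beside the rules for summary tables and well suited to describing participants. Sections 9.1.1 and 9.1.1.2 state their own reference, and a specific rule can govern a general one. The phrase in 5.1 and 5.2 can also mean the pre-treatment reading. Three hours lies within 3.5 hours. All of this stands. A reader might infer a flat contradiction in the baseline or incompatible measurement times, but the text shows only ambiguities that the plan leaves open.

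A reader might also infer that the fixed baseline produces false positive results at a calculable rate. The documents do not support that. They give no session schedule, no drift and no SD, and a non-device change within the hours after treatment would mislead the same-session comparison in the same way.

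On methods, it can be said that the SAP's confidence interval would cover a mean change, that 13.4.2.1 already has a general observed-values rule, and that the final plan could name a test. The first two are true, so description is possible. Neither supplies a test, a reference or a time, and 13.4.2.1 sends missing efficacy data to the censoring rule. A one-sample log-rank test against an external curve would be computable, but the plan names no such curve. The final plan could close the gap, but only if it is fixed before outcome data are reviewed.

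**Conclusion.** The plan is wrong as written on the main point: the stated efficacy outcomes have no applicable analysis, and the named primary test cannot be computed in one arm even for the events it was meant for. This follows from the text and needs no assumed values. It does not mean that the data could not be described, since the SAP's generic summaries would do that.

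The reference reading and the time window are secondary clarifications. The reference has no effect at the first session. At a later session it matters by b (absolute) or b + ab (percent), and the documents do not say how large b is or whether later sessions enter the analysis. The time wordings overlap but admit different readings. Choosing the same-session reference follows the comparison in 9.1.1 and 9.1.1.2. It does not remove the lack of a control.

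**What to change.** 1. In 13.7, replace the log-rank, Cox and censoring rules for SpO2, FVC and FEV1 with a paired analysis. Take percent change per participant, averaged over sessions specified in advance, and report the mean with its 95% CI and a two-sided 5% one-sample test on observed pairs, consistent with 13.4.2.1. Report how many enrolled participants have no complete pair. Present the event composite as a descriptive safety summary (number, percentage, Kaplan-Meier) without a log-rank test.
2. Before any outcome data are reviewed, have the sponsor reconcile which outcome is primary, since 5.1, 9.1, 9.1.1, 9.1.1.1, 9.1.2, 13.7, 13.7.1 and 13.7.1.1 differ. The two secondary endpoints of 13.7.1.2.4 also need naming: 9.1.1.2 includes surveys, and 13.7.2.1 lists nothing in the available text. Putting SpO2 first follows 5.1 but is not the only reading. Then align the Clinical Events Committee text in 6.4, 13.2, 13.7.2.1, 13.7.2.2 and Appendix 4. If surveys stay as a tested endpoint, they need their own method.
3. In 13.4.1.3, state that for these outcomes the reference is the reading before the same treatment session, and say which sessions count. Keep the pre-first-use reading for describing participants and for a descriptive trend over the 21 days.
4. Reconcile 5.1, 5.2, 9.1.1 and 9.1.1.2 to one post-treatment time with lower and upper limits, and time-stamp the readings.
5. State that the result is an uncontrolled before/after change and not a demonstrated device effect.

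The cost is wording in several sections and a time stamp on readings that participants already record on a smart device. Some early readings that 5.1 and 5.2 now allow may leave the main analysis, cumulative change becomes descriptive only, and the event composite loses its significance test.
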